## 2.3 Study design

This will be an interventional study with randomized control and open label trial. A parallel-group design with pre- and post-measurements (longitudinal design) will be employed, using subjective and objective measurements with questionnaires and structured interviews. It is a single center and national project.

The study consists of five phases:

1. Screening: Screening will be conducted by the applicant and master's students enrolled in the project who are bound to medical confidentiality, using electronic patient files at the hospital. The patients will be invited to the study by their treating physician or psychologist.

2. Pre-interventional measurement (1 session within the first week, max. 60minutes):

First, the psychopathological symptoms are to be assessed in order to decide about inclusion or exclusion (with PANSS; see also inclusion criteria). In addition, the therapeutic alliance and motivation for psychotherapy are measured. In order to record moderating effects or covariables, demographics (e.g. age, gender, education, years of illness) and two additional questionnaires will be added (attitude towards recovery and the individual motives).

3. Intervention (4 sessions within two weeks, 25- 40 minutes/session):

The patients receive either four sessions of motivational interviewing (intervention group) or four sessions of supportive counseling (control group). For Details see 2.4 "Study intervention"

4. Post-interventional measurement (1 session, max. 60 minutes): At the end of the intervention the motives, the negative symptoms, the hope for recovery, well-being and the level of functioning will be measured again.

The risk of bias should be kept at a minimum. Various precautions are being taken to this end.

- The most important confounding variables are controlled to prevent a bias.
- In order to avoid selection bias, patients are randomly assigned either to the intervention group or to the control group. Randomization is carried out at a 1:1 ratio, using pre-defined random lists (using the online randomization generator: <http://www.pub-med.de/tools/zufallsgenerator>) and a block schema prepared by the principal investigator.
- Block randomization ensures that the patients are distributed in the desired proportion to the two treatment modalities. All patients are randomized only once during the entire examination period.

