## 4 STATISTICS AND METHODOLOGY

### 4.1. Statistical analysis plan and sample size calculation

Hypothesis 1: Four sessions of motivational interviewing for newly admitted acute patients (within the first 7 days of hospitalization) improve the therapeutic alliance and the adherence for treatment compared to supportive counseling.

Statistical analysis for hypothesis 1: To apply the statistically most sensitive test, we will use an ANCOVA to analyze the treatment effect of motivational interviewing compared to supportive counseling, with baseline values used as covariates.

Hypothesis 2: Four sessions of motivational interviewing for newly admitted acute patients decreases symptom severity compared to supportive counseling.

Statistical analysis for hypothesis 2: We will use an ANCOVA to analyze the treatment effect of motivational interviewing compared to supportive counseling, with baseline values used as covariates.

Hypothesis 3: Patients show higher motivation to seek psychotherapeutic treatment and have a higher self-efficacy expectation after leaving the inpatient stay, when they received an intervention with motivational interviewing compared to supportive counseling.

Statistical analysis for hypothesis 3: We will use an ANCOVA to analyze the treatment effect of motivational interviewing compared to supportive counseling, with baseline values used as covariates.

Additional calculations: We also want to investigate how the number of hospitalization days and the severity of symptoms at the beginning of the intervention have an influence on the therapy outcome. We calculate this with a multiple regression with days of hospitalization and/or the PANSS total score as independent variables. The treatment outcome is defined as the delta between symptoms before and after the intervention and serves as dependent variable.

General statistical considerations: We will use routine procedures of data processing and use data transformation if necessary (in case of non-normal distribution). Standard statistical calculations will be computed. The level of significance will be set to  $p < 0.05$  (two tailed). Effect sizes will be calculated for significant results. The IBM® SPSS Statistics® statistical software as well as the program R will be used.

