Sample size justification: Comparable studies found effect sizes that were moderate (Cohen's  $d = 0.3 - 0.5$ ). An effect sizes of  $f = 0.25$  will require us to recruit at least 64 patients per group to achieve 80% power and to detect such an effect with reasonable certainty at an alpha level of 0.05. We therefore plan to include a minimum of  $N = 128$  patients (calculated with G\*Power 3.1).

Analysis population: There is only one analysis population for all hypothesis. For inclusion criteria see chapter 4.1.

Analysis of gender differences: Analyses of gender differences are not planned because there is no research evidence to suggest that gender may be a determining variable. However, it is planned to conduct a group comparison between patients who benefit strongly from MI and those who benefit little, and to investigate possible discriminatory factors as part of this.

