#### 4.2. Handling of missing data and drop-outs

All patients who completed the study will be taken into analysis. All collected data will be checked at each study assessment, and missing data will thus be avoided as much as possible. If missing data nevertheless does occur, data has to be excluded.

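### The search for factors behind benefit from MI compares strong with little benefiters, which cuts a continuous score at an unstated point and loses power against analysing it uncut

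*Combined protocol and SAP*

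**What the plan says.** Section 4.1 does not plan analyses by gender. It then adds that "it is planned to conduct a group comparison between patients who benefit strongly from MI and those who benefit little". The stated purpose is to look for factors that tell the two groups apart. The section does not say which outcome defines benefit, where the line between strong and little falls, whether patients in between are left out, which factors are examined, or what test is used.

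The outcomes in sections 2.2 and 3.3 (STAR, BARS, PANSS, FPTM, GSE) are all scores. The one patient-level treatment outcome that section 4.1 defines is also continuous: "The treatment outcome is defined as the delta between symptoms before and after the intervention and serves as dependent variable". That definition belongs to a separate analysis, which keeps the outcome whole: "We calculate this with a multiple regression with days of hospitalization and/or the PANSS total score as independent variables".

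The only power statement is for the comparison of the two arms: the assumed effect, f = 0.25, "will require us to recruit at least 64 patients per group to achieve 80% power". Alpha is 0.05, and the general considerations in section 4.1 make tests two-tailed.

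**The concern.** A split keeps only the side of the line on which each patient falls. A comparison of extremes also drops everyone in the middle. Either way, a factor that really relates to the outcome is harder to detect than if the score had been left whole. The factors that emerge also depend on where the line is drawn, and the plan leaves that open until the data are in.

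Power is short here to begin with, because the comparison concerns patients treated with MI, which is one arm. Section 1 says the results should feed into a larger multicentre trial, and a factor missed at this stage may not be carried forward. The plan gives no reason for cutting, and it already uses regression on an uncut outcome elsewhere in the same section.

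**Working it through.** **The plan's own figure.** With two groups, f = 0.25 is d = 0.5. The normal formula gives 2 × (1.960 + 0.842)² / 0.5² = 62.8, so 63 per arm. The noncentral t gives 79.5% power at 63 and 80.1% at 64 per arm, and an ANCOVA with one covariate gives 80.1% at N = 128. The stated 64 per group reproduces. It does not cover the benefit-group comparison, for which no power is stated.

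**Inputs for the check.** From the documents: two-sided alpha 0.05; allocation ("Randomization is carried out at a 1:1 ratio"); 64 per arm as the planning figure. Assumed, because the documents are silent: that all 64 MI patients are available, the correlation r between one factor and the benefit score, and the cut.

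**Formula.** Splitting a normal score with a proportion p on one side shrinks r to r × φ(z_p) / √(p(1 − p)). The multiplier is 0.399 / 0.5 = 0.798 at the median and 0.280 / 0.4 = 0.700 at 80/20. Power is approximately Φ(atanh(r) × √(n − 3) − 1.96).

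Example, r = 0.35, n = 64, √61 = 7.81:
- Uncut: 0.365 × 7.81 = 2.854, less 1.96 = 0.894, power 81%.
- Median split: r becomes 0.279, the product is 2.241, less 1.96 = 0.281, power 61%.
- 80/20 split: r becomes 0.245, the product is 1.953, less 1.96 = −0.007, power 50%.

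For modest r, the median split keeps about 0.798² = 0.637 of the information, as if 0.637 × 64 = 41 patients had been analysed whole. The 80/20 split keeps 0.70² = 0.49, or about 31 patients.

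**Simulation.** 20,000 MI arms of 64 per setting, one continuous factor. The uncut analysis is the correlation test. The cut analysis is a t-test of the factor between benefit groups (32 vs 32, or the outer 21 vs 21). The 80/20 column uses the formula. Power in %, loss in points in brackets:

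| r | Uncut | Median split | Outer thirds | 80/20 |
|---|---|---|---|---|
| 0.10 | 12.3 | 9.6 (2.7) | (1.7) | 8.5 (3.8) |
| 0.20 | 35 | 24 (11) | 28 (7) | 19.6 (15.7) |
| 0.30 | 68 | 48 (20) | 57 (11) | 38.4 (29.2) |
| 0.35 | 82 | 61 (21) | 71 (11) | 49.7 (31.7) |
| 0.40 | 92 | 75 (17) | 83 (9) | 61.3 (29.9) |
| 0.50 | 99.1 | 92.3 (6.8) | (2.7) | 81.4 (17.6) |

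Simulating the 80/20 split at r = 0.35 gives a loss of 31.9 points. The r that corresponds to the plan's f is 0.25 / √(1 + 0.0625) = 0.24, where power is 49% uncut, 32% with a median split and 39% with outer thirds.

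A binary factor present in half the patients also loses power, but less regularly, because the two-by-two test is discrete at this size. With a median split the loss is 0.3 points for a 0.3 SD difference and 6.9 points for 0.5 SD. With a 70/30 split it is 34.2 points for 0.7 SD. The ranges for a continuous factor are therefore illustrations, not bounds.

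**The case against.** The strongest objection is that the sentence specifies almost nothing. It attaches no test, so it could be read as a descriptive table, and it does not tie benefit to the symptom delta. This stands as a limit: that a score is being cut is an inference. It is a strong one, because the plan contains no binary endpoint or responder threshold from which such groups could otherwise be formed.

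A reader might infer that the plan gives up a fixed 7 to 21 points of power. The documents do not support that. The range follows from choosing r between 0.20 and 0.40 and two particular cuts. Contrasting strong with little benefit fits a comparison of extremes at least as well as a median split, and for outer thirds the loss over those correlations is only 7 to 11 points. Nor is 64 fixed: it is a minimum, and section 3.4 replaces withdrawn patients, while section 4.2 says "If missing data nevertheless does occur, data has to be excluded".

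A reader might also infer that the trial's conclusions are weakened. They are not. All three hypotheses are tested by ANCOVA on the full scores, and hospital days and PANSS total are already examined against the uncut delta. Only the wider, unnamed set of factors is affected.

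Finally, an uncut regression within the MI arm alone would be more powerful but would still not answer the question, because it cannot separate factors that modify the effect of MI from factors that predict improvement under either treatment. That is correct, and the change proposed here uses both arms for that reason.

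**Conclusion.** The concern holds as a minor point about an exploratory analysis. Grouping patients by degree of benefit cuts a continuous measure at an unstated place, and it lost power in every setting examined. With an assumed 64 MI patients and one continuous factor, the loss is about 7 to 21 points for r = 0.20 to 0.40 under a median split or outer thirds, and about 2 to 32 points over r = 0.10 to 0.50 and cuts up to 80/20. The width of that second range matters in itself: while the cut is open, so is how much the analysis can detect.

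The figures isolate the cost of cutting. They compare single-factor tests without baseline adjustment, and they do not give the power of the regression recommended below.

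**What to change.** In section 4.1, name the outcome that defines benefit and list the candidate factors. Replace the group comparison with a regression of the continuous post score on its baseline, arm, the candidate factors and factor-by-arm terms, using both arms. This extends the ANCOVA already planned for the hypotheses, and the factor-by-arm slope is what makes the result concern benefit from MI. Report slopes with 95% confidence intervals, labelled exploratory. A table of strong against little benefit can stay, without tests.

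The cost is a sentence or two of text, with no new patients, data or staff. There are two small downsides. Slopes are less intuitive for clinicians than two groups, which the descriptive table offsets. Interaction estimates will also be imprecise: ignoring the gain from baseline adjustment, and with outcome and factor in SD units, the difference between two arms' slopes has a standard error of about √(1/64 + 1/64) = 0.18, so a 95% interval of about ±0.35. That width comes from asking about benefit from MI specifically. Cutting the score would not avoid it.

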#### 4.2. Handling of missing data and drop-outs

All patients who completed the study will be taken into analysis. All collected data will be checked at each study assessment, and missing data will thus be avoided as much as possible. If missing data nevertheless does occur, data has to be excluded.

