### **2.2 Primary and secondary endpoints**

Primary endpoints are the therapeutic alliance as assessed with the *Scale to Assess Therapeutic Relationship STAR* (McGuire-Snieckus et al., 2007) and adherence to treatment as measured with the *Brief Adherence Rating Scale BARS* (Byerly et al., 2008). These variables will be measured before and after the study intervention or control intervention.

Secondary endpoints include changes in symptom severity as assessed with the *Positive and*

*Negative Symptom Scale PANSS* (Kay et al., 1987), as well as the motivation for psychotherapy (measured with the German version of the *Questionnaire to measure the motivation for psychotherapy* by Schulz et al., 1995) and self-efficacy (measured with the *General Self-Efficacy Scale* by Schwarzer & Jerusalem, 1995). All secondary variables will be measured before and after the study intervention or control intervention.

As this study (risk category A) does not include drugs or other medical products and patients are hardly exposed to any more risks than in routine clinical care, no safety endpoints are defined.

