#### Psychometric tests used in the study

Primary diagnosis at point of admittance and medical history are assessed by physicians and psychologists at PUK and documented electronically. The applicant and master's students enrolled in the project will use this available data and document them in specific study protocols. These assessments are part of standard assessments at the hospital by physicians and psychologists. For primary psychiatric diagnoses the International Classification of Diseases (ICD-10) is used.

- Psychotic symptoms are assessed with the *Positive and Negative Syndrome Scale* (PANSS). This is a structured interview, which consists of four scales measuring positive and negative syndromes of schizophrenia, their differential, and general severity of illness.
- Two cognitive tests: Letter-Number-Span (LNS), Symbol-Coding-Test (SCT) from MATRICS (Measurement and Treatment Research to Improve Cognition in Schizophrenia, Consensus Cognitive Battery; Nuechterlein et al., 2008)
- The *Brief Adherence Rating Scale* BARS (Byerly et al, 2008) is a brief, pencil-paper, clinician-administered adherence assessment instrument. It consists of 4 items: 3 questions and an overall visual analog rating scale to assess the proportion of doses taken by the patient in the past month (0%–100%).
- The therapeutic relationship will be evaluated with the *Scale to Assess Therapeutic Relationship* STAR (McGuire-Snieckus et al., 2007). The patient (STAR-P) and clinician scales (STAR-C) each have 12 items comprising three subscales: positive collaboration and positive clinician input in both versions, non-supportive clinician input in the patient version, and emotional difficulties in the clinician version.
- Motivation for psychotherapy will be measured with the *Fragebogen zur Erfassung der Psychotherapiemotivation* (FPTM; engl: "Questionnaire to measure the motivation for psychotherapy") by Schulz, Nübling und Rüdell (1995), a 4-point Likert-scale with 39 items.
- Self-efficacy is measured with the German version of the *General Self-Efficacy Scale* (GSE) by Schwarzer & Jerusalem (1995), an instrument that has been proved with a sample of more than 19'000 persons in 25 countries and shows good psychometric properties.

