### 3.4 Withdrawal and discontinuation

Participants have the right to abort the study at any point and without providing a reason. The principal investigator and the co-investigator have the right to withdraw participants if they knowingly provide incorrect information, withdraw consent, do not adhere to protocol requirements (i.e. missing appointments, ignoring instructions) or if the disease has progressed (see exclusion criteria).

If participants do not finish the experiment, the data will be stored properly and taken into analysis as far as possible and useful. Additional participants will be recruited to replace the withdrawn participants.

Since they are inpatients, there is a very low risk of missed appointments. If this is still the case, the appointments can be made up on the following day.

If participants are discharged before the end of the study, they may attend the remaining appointments as outpatients if the majority of the study has already taken place (at least 3 psychotherapy sessions must have taken place during inpatient treatment).

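### Exclusion is the only rule for missing data and its unit is not defined; read literally, one blank item can void a STAR or FPTM score, and a missing baseline discards an observed post score

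*Combined protocol and SAP*

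**What the plan says.** Section 4.2 makes three statements. The analysis set is completers: "All patients who completed the study will be taken into analysis". Gaps are to be prevented: "All collected data will be checked at each study assessment, and missing data will thus be avoided as much as possible". For gaps that remain, the rule is: "If missing data nevertheless does occur, data has to be excluded". The unit of exclusion is not named.

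The section on psychometric tests (within section 3.3) gives the lengths of the instruments. For STAR: "The patient (STAR-P) and clinician scales (STAR-C) each have 12 items comprising three subscales". FPTM is described as "a 4-point Likert-scale with 39 items". No scoring rule for incomplete forms is given for either, and no expected rate of unanswered items appears anywhere.

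STAR and BARS are the primary endpoints in section 2.2: "These variables will be measured before and after the study intervention or control intervention". FPTM, the General Self-Efficacy Scale (GSE) and PANSS are secondary and are also measured before and after. Section 4.1 analyses every hypothesis by ANCOVA with the baseline value as covariate, refers to a single analysis population, and sets a minimum of N = 128.

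Section 3.4 says of participants who do not finish that "the data will be stored properly and taken into analysis as far as possible and useful", and provides for replacing those who withdraw.

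**The concern.** This point is about completers with partly filled forms, not about drop-outs. If a blank item makes the scale score missing, and a missing score is excluded, a patient who answered 11 of 12 STAR items contributes nothing to a primary endpoint. The same happens when the baseline form is incomplete but the post score is fully observed. In a randomised comparison the baseline covariate serves precision only, so discarding the post score on that account is avoidable.

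These losses are not made up. Replacement under section 3.4 covers withdrawn participants, and a completer with an unusable score has not withdrawn. The sample size carries no allowance for unusable scores. If the unit of exclusion and the scoring rule are not fixed in advance, they will be chosen once the data are in hand.

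**Working it through.** **Inputs from the documents.** STAR has 12 items per version and FPTM 39 (section 3.3). There are two occasions (section 2.2), an ANCOVA with baseline covariate and two-sided alpha 0.05 (section 4.1), and f = 0.25 with 64 per group, N = 128, for 80% power (section 4.1).

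**Inputs assumed.** These are the item non-response rate p, the dependence between blanks within a patient, and the pre-post correlation r. None is in the documents.

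**Step 1: the plan's own figure.** Noncentral F test, numerator df 1, denominator df N − 3, noncentrality N f² = 128 × 0.0625 = 8.0. Power is 0.801, so N = 128 reproduces, with essentially nothing to spare.

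**Step 2: loss if one blank item voids a score, blanks independent.** Both visits are needed, so the share of pairs lost is 1 − (1 − p)^24 for STAR (2 × 12) and 1 − (1 − p)^78 for FPTM (2 × 39). Power is recomputed as in step 1 on the remaining N, with f held at 0.25 (that is, r = 0).

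| Assumed p | STAR lost | N left | Power | FPTM lost | N left | Power |
|---|---|---|---|---|---|---|
| 0.1% | 2.4% | 125 | 0.79 | 7.5% | 118 | 0.77 |
| 0.5% | 11.3% | 113 | 0.75 | 32.4% | 87 | 0.64 |
| 1% | 21.4% | 101 | 0.70 | 54.3% | 58 | 0.46 |
| 2% | 38.4% | 79 | 0.59 | 79.3% | 26 | 0.23 |

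**Step 3: blanks clustered within patients.** Beta-binomial with an assumed intra-patient correlation of 0.1, so α = 9p and β = 9(1 − p). The chance of no blank in m items is the product over i = 0 to m − 1 of (β + i)/(α + β + i). At p = 1%, α = 0.09 and β = 8.91. The loss is 11.4% for STAR (m = 24; N left 113, power 0.75) and 18.9% for FPTM (m = 78; N left 104, power 0.71).

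**Step 4: a useful baseline covariate.** If f = 0.25 refers to the unadjusted SD and r = 0.5, the effective f is 0.25/√(1 − 0.25) = 0.289. Power is then 0.90 at N = 128, about 0.82 for STAR at N = 101 (the 1% row) and 0.58 for FPTM at N = 58. The power columns in step 2 are therefore worst cases.

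**Step 5: what the remedies recover.**
- Keeping patients whose only gap is the baseline leaves the post form alone at risk. At p = 1% the loss is 1 − 0.99^12 = 11.4% for STAR instead of 21.4%, and 1 − 0.99^39 = 32.4% for FPTM instead of 54.3%.
- Proration with at least 80% of items answered means 10 of 12 for STAR (0.8 × 12 = 9.6) and 32 of 39 for FPTM (0.8 × 39 = 31.2). With independent blanks at p = 1%, the binomial probability of exceeding the limit is 0.02% per STAR form and practically zero per FPTM form. Even at p = 2%, the share of pairs lost is 0.3% for STAR and about 0 for FPTM.
- With the clustering of step 3, proration recovers slightly less. At p = 1% the chance that at least one of the two forms exceeds the limit is about 1.7% for STAR and 1.2% for FPTM. These figures ignore the further condition in the fix that no subscale be wholly blank.

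**The case against.** The strongest reply is that the plan does not say that a questionnaire is thrown away for one blank item. A reader might infer that from section 4.2, or infer that the whole patient is dropped because section 4.1 speaks of one analysis population. The sentence supports neither as fact, since it names no unit. It could also mean that only the blank item is left out. That stands, and it is why the point is an undefined unit and a missing scoring rule. It does not dispose of the matter: leaving out only the blank item gives a total that is not comparable with a full one unless it is rescaled, and no rescaling rule exists.

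Second, a large loss cannot be read from the documents. Forms are checked at each assessment, which should keep p low. At 0.1% only 2.4% of STAR pairs and 7.5% of FPTM pairs go. Independence overstates the loss when blanks concentrate in few patients, and r = 0 is the least favourable case for an ANCOVA. All of that stands. The check reduces the number of blanks but leaves the rule for the remainder unchanged, and section 4.2 itself anticipates that some will remain.

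Third, the heaviest losses fall on FPTM, which is secondary, and BARS is a short clinician-administered instrument for which no loss is shown. This also stands, with one reservation. Section 3.3, on expected biases, says that baseline motivation for psychotherapy will enter the calculations. If it entered the STAR model, 24 + 39 = 63 items would have to be complete, and the loss at p = 1% would be 1 − 0.99^63 = 47% under independence. Section 4.1 names only the baseline values as covariates, so this is conditional.

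Fourth, section 3.4 shows an intention to use partial data. That wording concerns participants who do not finish, and it fits poorly with the completers-only sentence in section 4.2.

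A reader might also infer that the analysed set would drift towards less ill patients. That is plausible, but nothing in the documents shows it, and the point does not need it.

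**Conclusion.** The concern holds in a limited form. It is certain that exclusion is the only stated rule, that its unit is undefined, and that no scoring rule for incomplete scales is given. Followed literally, the rule loses observed data that standard scoring would keep, so this is more than missing detail.

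The size is uncertain. For assumed item non-response between 0.1% and 1%, the loss of STAR pairs runs from 2% to 21% if blanks are independent, and is about 11% at the top of that range with the assumed clustering. For FPTM the corresponding figures are 7.5% to 54%, and about 19%. The power figures at r = 0 illustrate the worst case and are not forecasts: with r = 0.5, STAR keeps about 82% power even at the 1% independent rate. The change should be made because it is cheap and removes a choice that would otherwise be made after the data are seen. The documents do not show that the trial will lose a large share of its scores.

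**What to change.** Replace the last sentence of section 4.2 with:

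> Exclusion applies only to the endpoint affected, not to the patient. Incomplete multi-item questionnaires (STAR, FPTM, GSE) are scored by the instrument's own rule for missing items. Where there is none, each subscale is prorated from its answered items, after reverse-scoring, when at least 80% of the items of the scale are answered and no subscale is wholly blank. BARS is not prorated. A patient with an observed post score and a missing baseline stays in the ANCOVA with the baseline set to the pooled mean and a missing indicator.

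Proration is by subscale because STAR combines subscales that point in different directions (positive collaboration against non-supportive input or emotional difficulties), so a whole-scale mean could fill a blank from the wrong construct. BARS is left out because averaging three questions with a 0–100% rating has no clear meaning. The 80% threshold is a convention and gives way to a published scoring rule.

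The cost is a few sentences and a few lines of syntax, with no added visit, form or patient burden. The small downside is that proration assumes the answered items represent the blank ones.
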